8.2.2 Exclusion Criteria

1. Evidence of neovascular AMD by history, as well as by clinical exam, fluorescein angiography (FA), or ocular coherence tomography (OCT) at baseline in either eye.
2. History or presence of diabetic retinopathy, vascular occlusions, uveitis, Coat's disease, uncontrolled glaucoma, cataract or media opacity preventing posterior pole visualization or any significant ocular disease other than AMD that has compromised or could compromise vision in the study eye and confound analysis of the primary outcome.
3. History of retinal detachment repair in the study eye.
4. Axial myopia greater than -6 diopters.
5. At least 2 months following cataract removal in the study eye and Yttrium Aluminum Garnet (YAG) laser capsulotomy in the study eye in the past 4 weeks and any other ocular surgery in the study eye in the past 3 months prior to OpRegen implantation.
6. History of cognitive impairments or dementia.
7. Contraindication for systemic immunosuppression.
8. History of any condition other than AMD associated with choroidal neovascularization in the study eye (e.g. pathologic myopia or presumed ocular histoplasmosis).
9. Any type of systemic disease or its treatment, in the opinion of the Investigator, including any medical condition (controlled or uncontrolled) that could be expected to progress, recur, or change to such an extent that it may bias the assessment of the clinical status of the patient to a significant degree or put the patient at special risk.
10. For female subjects; pregnancy or breastfeeding.
11. Current participation in another clinical study. Past participation (within 6 months) in any clinical study of a drug administered systemically or to the eye.
12. Currently receiving aspirin, aspirin-containing products and/or any other coagulation modifying drugs which cannot be discontinued 7 days prior to surgery.
13. History of cancer (other than a non-melanoma skin cancer). For cancers in remission more than five years, enrollment is allowed with concurred documented approval of principal investigator and oncologist prior to enrollment.⁵

Note: "Live" attenuated vaccination is prohibited during active systemic immunosuppression.

⁵ In the case of any suspected malignancies at screening, patient should be referred to appropriate medical specialist.

8.3 ELIGIBILITY CRITERIA FOR COHORT 4

8.3.1 Inclusion Criteria

1. Age 50 and older.
2. Diagnosis of dry (non-neovascular) AMD in both eyes.

[REDACTED]

11. BCVA letter score of ≥ 29 letters and ≤ 64 letters (Snellen equivalent of 20/64 – 20/250) in treated eye using ETDRS charts at starting distance of 4m.
12. Visual acuity as measured by ETDRS in the non-operated eye must be better than or equal to that in the operated eye.
13. Subjects with sufficient good health that can participate in all study-related procedures and complete the study follow-up period (based on medical records).
14. Ability to undergo a vitreoretinal surgical procedure under monitored anesthesia care.
15. Blood counts, blood chemistry, coagulation and urinalysis without abnormal significance.
16. Negative for TB, HIV, HBC, and HCV. Negative for acute or reactivated CMV IgM and EBV IgM or asymptomatic in the opinion of the investigator.
17. Willing to defer donation of blood and tissues.
18. Able to understand study procedures and willing to sign informed consent.

8.3.2 Exclusion Criteria

1. Evidence of neovascular AMD by history, as well as by clinical exam, fluorescein angiography (FA) at ocular coherence tomography (OCT) at baseline in either eye.

[REDACTED]

[REDACTED]

8. At least 2 months following cataract removal in the study eye and Yttrium Aluminum Garnet (YAG) laser capsulotomy for both eyes. Any other ocular surgery in either eye in the past 3 months prior to OpRegen implantation.
9. Current participation in another clinical study of an active drug (placebo and sham will be allowed). Past participation (within 6 months) in any clinical study of a drug administered systemically (except for vitamins and minerals) or to the eye.
10. History of cognitive impairment or dementia

11. Contraindication for systemic immunosuppression
12. Any type of systemic disease or its treatment, in the opinion of the Investigator, including any medical condition (controlled or uncontrolled) that could be expected to progress, recur, or change to such an extent that it may bias the assessment of the clinical status of the patient to a significant degree or put the patient at special risk.
13. For female subjects; pregnancy or breastfeeding
14. Currently receiving aspirin, aspirin containing products and/or any other coagulation modifying drugs which cannot be discontinued 7 days prior to surgery
15. History of cancer (other than a non-melanoma skin cancer). For cancers in remission more than five years, enrollment is allowed with concurred documented approval of principal investigator and oncologist prior to enrollment.⁶
16. Known allergy to any of the study medications or formulation.
17. Inability to comply with study or follow-up procedures
18. Inability to obtain CFP, FAF, OCT/OCTA and microperimetry of sufficient quality to be analyzed and graded by the Central Reading Center

Note: "Live" attenuated vaccination prohibited during active systemic immunosuppression.

Final decision for subject eligibility upon confirmation of Central Reading Center and the Sponsor.

9. CONCOMITANT MEDICATIONS AND SUPPORTIVE CARE

9.1 PREVIOUS MEDICATIONS

All medications taken by/given to the subject, as a treatment for the primary and concomitant diseases within two weeks prior to the subject screening visits, will be recorded in the case report form (CRF). Change in these medications should be recorded during each subsequent subject evaluation.

9.2 DISALLOWED CONCOMITANT MEDICATIONS

The subjects should be instructed to discontinue medications that may alter coagulation, including aspirin and aspirin-containing medications, 7 days prior to the implantation of OpRegen. They should be guided to discuss the risks associated with this discontinuation with their primary physician. Decisions regarding the timing of restarting these medications will be at the discretion of the Principal Investigator.

Anti VEGF intraocular injections are contraindicated when given as a treatment for Wet AMD. However, if subject was treated with Anti VEGF intraocular injections as a short-term therapy for an indication other than Wet AMD (or disease which is defined as exclusion criteria) more than

⁶ In the case of any suspected malignancies at screening, patient should be referred to appropriate medical specialist.

12 months prior to study baseline, patient may be eligible after being discussed with Study Medical Monitor.

9.3 PER PROTOCOL STUDY MEDICATIONS

9.3.1 Immunosuppressive Medications

Subjects undergoing an allogeneic cell transplantation procedure may develop an immune response towards these cells, thereby limiting their survival and functionality. Therefore, the subjects will receive systemic immunosuppression therapy [REDACTED]

[REDACTED]
and long-term systemic treatment.

9.3.1.1 [REDACTED]

[REDACTED]

[REDACTED]

[REDACTED]

[REDACTED]

[REDACTED]

9.3.1.2 **Systemic (PO) tacrolimus**

Systemic (PO) tacrolimus 0.01 mg/kg daily [REDACTED]

[REDACTED] up to 6 weeks post-transplantation, [REDACTED]

9.3.1.3 **Systemic (PO) mycophenolate mofetil,**

Systemic (PO) mycophenolate mofetil, up to 2gr/per day, [REDACTED]

[REDACTED] for at least three months [REDACTED] post-transplantation, [REDACTED]

9.3.2 **Pupillary Dilation**

It is recommended that all subjects whenever possible will undergo a pupillary dilation to a minimum of 8 mm during ophthalmological assessment. This will allow better quality imaging. A proven method is the instillation of 1-2 drops of 0.5% tropicamide (or equivalent) followed by 1 drop of 10% phenylephrine (or equivalent). Subjects with heavily pigmented irises will take longer to achieve full dilation.

9.3.3 **Prophylaxis and Treatment of Infections**

Institution guidelines will be followed to provide prophylaxis for infections. Strict guidelines for hygiene and care will be applied. Topical antibiotic treatment as customary following vitrectomy procedure will be given, including a course of topical antibiotic drops (ofloxacin or equivalent 4 times daily) beginning the day after surgery and over the course of up to 6 weeks.

Subjects subjected to the immunosuppressive treatment outlined in this study may develop immunodeficiency. Therefore, the approach to the diagnosis and treatment of fever in such subjects should be an aggressive one. If any infections occur, they will be treated per institutional practice and will be documented as adverse events (AEs).

9.3.4 **Contrast Imaging Drug**

Fluorescein a 5 cc (ml) solution of 10% sodium fluorescein will be given prior to FA imaging. The injection should be performed in an antecubital vein with a 19 or 21-gauge butterfly infusion. A vein in the hand may be used if no access can be obtained in the antecubital region.

9.3.5 **Supportive Care**

Subjects should receive full supportive care according to the Institution's practice patterns and clinical guidance, including analgesic, antibiotic, anti-inflammatory and antipyretic medications, or any other supportive care according to clinical judgment.

[REDACTED]

All concomitant medications administered, from time of signature on the informed consent and until the end of the study, will be recorded in the CRF and the reason for administration should be clearly stated in the indications and if needed also documented as AEs.

Rescue equipment (oxygen) and drugs such as hydrocortisone, epinephrine (or other inotropic agents), and antihistamines should be available at the surgery unit and will be administered per investigator discretion.

9.3.6 Per Protocol Medication Return

Every effort will be done to assure that subjects return any unused per protocol medications to the site.

10. STUDY DESIGN

This clinical trial will evaluate the safety, tolerability and preliminary efficacy of subretinal implantation of OpRegen to subjects with advanced form of dry-AMD. The study will consist of four cohorts. The first 2 cohorts, 3 subjects each, legally blind with best corrected visual acuity of 20/200 or worse in the study eye, will receive a single subretinal implantation of OpRegen. The third cohort will include up to 6 subjects, with BCVA of 20/200 or worse in the study eye, will receive a single subretinal implantation of OpRegen. The fourth cohort will include approximately 12 subjects with BCVA between 20/64-20/250, of whom 6 will receive a targeted single subretinal implantation of OpRegen [REDACTED]. Staggered intervals within and between cohorts will be applied, as described in Sections 6.5 and 10.1. The study is being conducted in participants with confirmed bilateral GA (Study Eye and Non-Study Eye). Between cohorts, and subjects if applicable, the next step to proceed will occur per DSMB recommendation, based on accumulated safety data.

Cell suspension will be delivered into the subretinal space in the macular area as described in the IFU and operating manuals for each delivery device. A total volume of up to [REDACTED] cell suspension (depending on the dose) will be implanted in single area at potential risk for GA expansion. Along with the relevant surgical procedure, the subjects will receive systemic immunosuppression [REDACTED], as described in Section 9.3.

During Part 1 of the study, subjects will be assessed at pre-scheduled intervals, as shown in Table 2 using methods and techniques described in Table 1. The study evaluation plans are designed to assess occurrence of systemic adverse events and to detect potential toxicities in different organ systems. Furthermore, ophthalmological examination and visual and retinal functional and structural examinations will be performed as part of baseline assessment and during follow-up, in order to collect initial data about the efficacy of OpRegen.

An end of Part 1 of the study visit is planned at [REDACTED] after the implantation of OpRegen.

[REDACTED]

10.1 DOSE ESCALATION AND STAGGERED INTERVALS

Staggered intervals between subjects within each cohort and between cohorts were designed in order to allow monitoring and investigation of adverse events, prior to exposing additional subjects to the product.

The safety data gathered from each cohort will be reviewed by the independent Data Safety Monitoring Board (DSMB, see Section 20.2). Depending on the safety data there will be a DSMB recommendation to pursue one of the following alternatives: proceed to the next higher dose; stop dose escalation; investigate a lower dose; or repeat a dose level.

The staggered procedure that will be followed in this study is described below.

[REDACTED]

10.2 DOSE LIMITING TOXICITY (DLT) AND STOPPING RULES

Potential toxicities and safety issues associated with the surgical procedure and of the investigational product will be carefully monitored during this study.

Stopping Rules

[figure not shown]

Figure 2: Stopping Rules

Based on the toxicity scales presented in Section 21.1.7 (see Table 6 and Table 7), the stopping rules (Figure 2) are defined as follows:

- 2 subjects with Grade 3 ocular toxicity, except cataract, or
- One (1) subject with Grade 4 ocular toxicity, except cataract, or
- 2 subjects with Grade 3 systemic toxicity, or
- One (1) subject with Grade 4 systemic toxicity

Based on the ocular toxicity scale presented in Section 21.1.7 (see Table 6) the dose limiting toxicity are defined as follows:

- 2 subjects with Grade 3 ocular toxicity, related to the investigational product except cataract, or
- One (1) subject with Grade 4 ocular toxicity, related to the investigational product except cataract

In case a Grade 3-4 toxicity occurs during the dosing within a cohort, as defined above, in accordance with the stopping rule, the dosing of the next subjects will be postponed until a decision is made by the DSMB regarding the relation of the SAE to OpRegenand to the surgical procedure. If, according to the DSMB opinion, the SAE is not related to the investigational product and the implantation procedure, the dosing schedule of the next subjects will be continued according to the

study plan. In case the event is related to the investigational product and the implantation procedure (dose limiting toxicity), dose adjustment and/or surgical procedure modification will be performed in accordance with recommendations of the DSMB.

The study sponsor is ultimately responsible for all decisions.

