21. SAFETY REPORTING

21.1 ADVERSE EVENTS DEFINITION

A clinical trial AE is any untoward medical event associated with the use of a drug or drug delivery system in humans, whether or not it is considered related to a drug or drug delivery system, or due to per protocol medications received.

A lack of drug effect is not an AE in clinical trials because the purpose of clinical trials is to establish whether there is drug effect and the nature of that effect or lack thereof.

AEs may be either spontaneously reported or elicited during questioning and examination of the subject. The occurrence of an AE will be determined on the basis of observed or volunteered signs and symptoms and changes in the subject's physical examination and laboratory test results.

During the study, site personnel will record any change in the condition(s) and the occurrence and nature of any AEs on the source documents and on the appropriate AE CRF. AE is any symptom, sign, illness or experience that develops or worsens in severity during the course of the study or through the long-term follow up period. Intercurrent illness or injuries will be considered as AEs. Abnormal results of diagnostic procedures will be considered as AEs if the abnormality:

- Results in study withdrawal

- Is associated with SAE
- Is associated with clinical sign or symptom
- Leads to additional treatment or to further diagnostic tests
- Is of clinical significance, as considered by the study Investigator

Preexisting condition is one that is present at the start of the study. Preexisting conditions will be recorded as AEs if their frequency and/or intensity worsens during the study period. At baseline evaluations, any clinically significant abnormality will be recorded as a preexisting condition at medical history. All new signs and symptoms will be reported as AEs.

The recording period for AEs starts at the time of written informed consent until the subject completes the study, unless an unresolved AE is still being followed-up. For all subjects who took at least one dose of study drug/ per protocol medications – whether they completed the treatment period or not – the recording period ends 4 weeks/28±4 days after study termination/completion.

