Cataract	Mild change from baseline, detected on ophthalmologic examination, not warranting intervention	Moderate change from baseline, detected on ophthalmologic examination, not warranting intervention	Severe change from baseline, detected on ophthalmologic examination, not warranting intervention NOT SAE	Severe change warranting operative intervention NOT SAE
Uveitis	Mild anterior uveitis, not warranting intervention	Moderate anterior uveitis, warranting intervention	Severe posterior or pan-uveitis, warranting medical intervention	Severe uveitis warranting operative intervention and threatening ocular integrity
Vitreous hemorrhage	Mild hemorrhage detected on ophthalmologic examination, not warranting intervention	Moderate hemorrhage not warranting intervention	Severe hemorrhage warranting vitrectomy	Uncontrolled vitreous hemorrhage, threatening ocular integrity
Retinal detachments/PVR (Proliferative vitreoretinopathy)	Localized, peripheral intervention not indicated	Not resolving; intervention not indicated	Operative intervention indicated	Operative failure, threatening ocular integrity

Systemic toxicity will be graded based on the scale, shown in [Table 7](#).

The following AEs are defined as systemic toxicity and are to be assessed for grading as follows:

Table 7. Systemic toxicity scale

Grade	Definition
1	Mild toxicity, usually transient, requiring no special treatment and generally not interfering with daily activities.
2	Moderate toxicity which may be ameliorated by simple therapeutic maneuvers, and impairs usual activities
3 SAE	Severe toxicity which requires therapeutic intervention and interrupts usual activities. Hospitalization may or may not be required.
4 SAE	Life-threatening toxicity which requires hospitalization

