## 6.0 STATISTICAL ANALYSIS GENERAL CONSIDERATIONS

The planned sample size of 24 treated eyes, [REDACTED], with targeted doses of  $50 \times 10^3$  and up to  $200 \times 10^5$  cells, is considered clinically appropriate for further characterization of the safety, tolerability, and preliminary efficacy of OpRegen in the treatment of subjects with advanced dry-form [AMD](#) with [GA](#).

Comprehensive interim reports of accumulated safety, tolerability and preliminary available efficacy data were presented to the [DSMB](#) prior to escalation to the next to come study dose and to enrolment of the next to come study cohort. Between cohorts, and subjects when applicable, the next step to proceed occurred per [DSMB](#) recommendation based on accumulated safety data.

All measured variables and derived parameters will be listed individually and if appropriate, presented in summary tables by dose regimen group and overall, providing sample size, absolute and relative frequency for categorical variables, or sample size, arithmetic mean, standard deviation, median, minimum, and maximum for continuous variables. [Confidence intervals](#) will be presented for the efficacy endpoints for exploratory purposes only. Complete analyses to be prospectively performed are outlined in this SAP.

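### After a pause for Grade 3-4 systemic toxicity, the Section 10.2 restart test asks only about OpRegen and surgery, so an event attributed solely to immunosuppression meets the written condition to continue dosing

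*Protocol*

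**What the plan says.** Protocol Section 10.2 has four stopping criteria, two ocular and two systemic. The systemic ones are Grade 3 toxicity in two subjects, or "One (1) subject with Grade 4 systemic toxicity". Neither carries a cause qualifier. The dose-limiting toxicity criteria in the same section, by contrast, are restricted to events related to the investigational product.

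Once a criterion is met, the next subjects wait until the DSMB has decided how the SAE relates to OpRegen and to the surgical procedure. There are two branches:

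- If the DSMB considers that "the SAE is not related to the investigational product and the implantation procedure, the dosing schedule of the next subjects will be continued" under the existing plan.
- If the event is related, "dose adjustment and/or surgical procedure modification will be performed in accordance with recommendations of the DSMB".

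The section's opening sentence sets the same scope: toxicities of the surgery and of the investigational product. The sponsor keeps final responsibility for decisions.

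Immunosuppression is handled elsewhere. Section 9.3.1 lists tacrolimus and mycophenolate mofetil among the per protocol study medications, and Section 10 says they are given along with the surgery. Section 21.1 defines an adverse event "whether or not it is considered related to a drug or drug delivery system, or due to per protocol medications received". Section 21.1.7 introduces the systemic scale in Table 7 with "The following AEs are defined as systemic toxicity and are to be assessed for grading as follows", and labels Grades 3 and 4 as SAEs.

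**The concern.** The pause is broad and the restart test is narrow. Any cause of Grade 3-4 systemic toxicity can stop dosing at the stated counts, but the written condition for resuming looks at only two causes. The cause left out is a systemic treatment that every subject is due to receive, and the protocol itself expects trouble from it. Section 9.3.3 warns of immunodeficiency, calls for an aggressive approach to fever and requires infections to be recorded as adverse events. Section 19.5 lists immunosuppression as a risk needing its own protection.

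What is at stake is the safety of subjects still to be dosed in a cohort. After a life-threatening infection put down to the regimen, the specific rule in 10.2 points towards carrying on unchanged. It neither asks the DSMB about the regimen nor offers a change of regimen as a response.

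**Working it through.** The plan states no figure on this point, so the check is to apply the rule, as written, to one case: a Grade 4 systemic event due solely to immunosuppression.

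1. **Is it captured and graded?** Yes. The adverse event definition in 21.1 extends to per protocol medications, and Table 7 grades systemic events without regard to cause. Grade 4 is life-threatening toxicity requiring hospitalization. Grade 3 needs only therapeutic intervention and interrupted usual activities, with or without hospitalization.

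2. **Does it start the pause?** Yes. One subject is enough, and no cause is specified. Two subjects with Grade 3 events of the same origin also suffice. A single Grade 3 event does not.

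3. **Could immunosuppression fall under one of the two named causes?** Not on the documents' own terms.
   - Section 18.1 describes OpRegen as the cell product alone.
   - Section 10 gives immunosuppression alongside the surgery, not as part of it.
   - The early-termination text in 21.1.2 names study drug, per protocol medication and protocol procedure separately.
   - SAP Table 14.3.1.4.2 tabulates adverse events by relationship to per protocol treatment, so the omitted cause is already recognised.

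4. **Which branch applies?** The continue branch. Its wording joins the two causes with *and*, which could mean related to neither or not related to both together. An event due only to immunosuppression satisfies either reading, so the result does not depend on that ambiguity.

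5. **Do the other escalation rules catch it?** No. Section 22.14 counts dose-limiting toxicities towards exceeding the MTD, and 22.13 defines these as product-related SAEs. The DSMB alternatives in 10.1 and 22.4 all concern cell dose: go higher, stop escalating, go lower or repeat.

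**Extent.** Two of the four stopping criteria are affected. With cohort sizes of 3, 3, up to 6 and about 12, the most subjects left to dose after a Grade 4 event in the first subject is n - 1:

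| Cohort | n | n - 1 |
|---|---|---|
| 1 | 3 | 2 |
| 2 | 3 | 2 |
| 3 | 6 | 5 |
| 4 | 12 | 11 |

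These are ceilings that assume one-at-a-time dosing. For Cohort 4 the Synopsis promises staggering only between at least the first two subjects of each delivery modality. The counts show how many subjects a restart decision could reach, not how likely it is to be needed.

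**The case against.** The strongest reply is that the restart test matches the section's own scope. Section 10.2 opens by limiting itself to the surgery and the product, and immunosuppression has a separate pathway. Contraindication to it is an exclusion criterion, and a study-dedicated investigator or designee follows its adverse reactions (19.5). The Synopsis has the agents modified in consultation with the Medical Monitor when side effects cannot be controlled. That explains the wording, but the systemic criteria in the same section still reach beyond this scope, and the restart test does not follow them.

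The second reply is that the DSMB is not bypassed, and this stands. Dosing resumes only after a DSMB decision, so it would be wrong to infer that it resumes by itself. Section 10 adds: "Between cohorts, and subjects if applicable, the next step to proceed will occur per DSMB recommendation, based on accumulated safety data". SAP Section 6.0 reports this in the past tense: "Between cohorts, and subjects when applicable, the next step to proceed occurred per" DSMB recommendation. Section 21.3.2 sends Grade 3-4 toxicities to the DSMB without an attribution filter, Section 20 has SAEs evaluated immediately by the Medical Monitor and the DSMB, and Section 20.2 lets the board recommend stopping for safety. A reader might conclude that the trial has no safeguard against this case; these provisions show otherwise. They can close the gap, but none is written as a restart condition.

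Third, Figure 2, parts of 9.3.1, 10.1 and 19.3-19.4, and the DSMB charter could not be read. Any of them may supply the missing condition, so the documents do not support saying that the plan as a whole lacks one.

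Two other inferences also fail. One is that a waiting subject would not yet have begun immunosuppression: its start relative to implantation is redacted, and it is prescribed once a subject is found eligible. The other is that the Medical Monitor route covers only the affected subject: the Synopsis does not say so.

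**Conclusion.** The point holds as a mismatch inside Section 10.2: the written condition for continuing is narrower than the trigger for pausing. A Grade 3-4 systemic event that the DSMB attributes solely to immunosuppression literally meets that condition, and the actions listed in the section do not include changing the regimen for later subjects.

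This rests on the readable text of 10.2, on treating immunosuppression as distinct from both the product and the implantation procedure, and on the event being attributed to immunosuppression alone.

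It is minor. No endpoint or analysis changes. SAP Section 4.0 describes all 24 subjects as dosed, so the wording matters only for further dosing under this rule. Nothing in the documents shows that such an event occurred or that a subject was dosed wrongly because of it. It remains worth correcting because a stated rule can point to the wrong action, and the correction is cheap.

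**What to change.** In Section 10.2:

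- Extend the DSMB's causality question to the investigational product, the implantation procedure, or per protocol medication (immunosuppression).
- Resume dosing on the unchanged plan only if the DSMB considers the event related to none of these.
- Add modification of the immunosuppressive regimen for subsequent subjects to the listed actions.

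Mirror the change in Figure 2 and the DSMB charter if they repeat the rule. The cost is a wording amendment; attribution to per protocol treatment is already planned for tabulation in SAP Table 14.3.1.4.2. The downside is that some pauses may last longer while the DSMB considers the regimen.
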